	
Primary outcomes: opioid use, and symptom burden measured by M. D. Anderson Symptom Inventory – Bone Marrow Transplantation (MDASI-BMT).
 
Secondary outcomes: Brief Pain Inventory–Short Form, Patient-Reported Oral Mucositis Symptom Scale, Pain Medication Side Effects Questionnaire quality of life measured by Patient-Reported Outcomes Measurement Information System – 29 Items (PROMIS-29).
 
Other outcomes: opioid dose, clinical features (diagnosis and disease status), Common Terminology Criteria for Adverse Events Version 5.0 (CTC-AE v5.0), Opioid Risk Tool, Acupuncture Expectancy, use of health care resources (length of hospital stays during HSCT, transfers to the intensive care unit (ICU) while hospitalized, urgent care/emergency room visits, and readmission rates during the first 30 days post-HSCT).

Analytic Methods	All analyses will be by intent-to-treat, with patients entered into analysis as randomized, irrespective of treatment actually received. For Aim 1 opioid use, we will utilize logistic regression to model the probability of opioid use at specific time points (i.e., day 7 and 90, separately), and generalized linear mixed models to model the probability of opioid use across all time points (i.e. days 7, 15, 30, and 90), as a function of study arm (ACU vs. OPI), time, and randomization stratification variables. For Aim 1 symptom burden and Aim 2 pain, side effects and QOL , we will use linear mixed models to similarly model those continuous endpoints over time. We will also explore potential causal mechanisms by testing mediation hypotheses (e.g. test whether the effect of treatment on Day 90 opioid use is mediated through the effect of treatment on Day 7 opioid use).
Funding Source	Peer-reviewed Patient-Centered Outcomes Research Institute (PCORI) contract

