## 7.2 Randomization

After registration, research staff will randomize patients via MSK's secure Clinical Research Database (CRDB) using permuted blocks of random length. The allocation ratio will be 1:1 for ACU:OPI. Using the institutional randomization standard procedure with random blocks for RCTs will ensure full allocation concealment. Randomization will be stratified by study site, primary cancer diagnosis (MM versus HD versus NHL) and transplantation setting (inpatient versus outpatient) to ensure these characteristics are comparably distributed between the two study arms.

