In our pilot study, among “opioid-naïve” patients, 25% of sham acupuncture (SA) patients and 7% of true acupuncture (TA) patients were opioid users at Day 90. For our sample size/power estimates for Aim 1, we conservatively assume that patients in the OPI arm will have similar Day 90 opioid usage (25%) as the SA patients in our prior study, and that 10% of patients in the ACU arm will be using opioids at Day 90 (slightly higher than the TA arm in our pilot study). This translates to a relative reduction of 60% fewer opioid users in the ACU arm, and an odds ratio of 0.33, which would be considered clinically meaningful. The attrition rate was only 5% in our pilot study. However, we will conservatively plan for a high 10% attrition rate by randomizing 300 patients (150 per arm) in order to obtain 270 patients (135 per arm) with evaluable Day 90 endpoints. With an initial sample size of 300 patients and a 10% attrition rate, we will have 81% statistical power to detect this Day 90 difference between the two arms (i.e. 10% vs 25%) at a significance threshold of  $p<0.02$  using logistic regression analysis and a two-sided significance test. It is possible that the OPI group will have higher opioid use than the SA patients in our pilot study, as sham acupuncture is known to have some placebo effect. We therefore expect a larger effect size than we observed in the pilot study where true acupuncture was compared to sham acupuncture. In that scenario, assuming 30% in the OPI group use opioids versus 10% in ACU group, our power will increase to 96%.

We based our sample size exclusively on having adequate power for the Day 90 comparison of opioid use. This was due to the high public health priority to find pain interventions that can reduce long-term opioid use. That said, we expect the Day 7 comparison to have similar power as the Day 90 comparison. We believe this is a conservative assumption, and that we most likely have higher power at Day 7 due to lower attrition and potentially a larger effect size at Day 7 relative to Day 90. For example, in our pilot study, 20% of sham acupuncture (SA) patients were using opioids at Day 5 (opioid usage not collected at Day 7) compared to none of the true acupuncture (TA) patients.

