## 14.2. Statistical Methods.

**14.2.1. General Approaches.** All analyses will be by intent-to-treat, with patients analyzed as randomized, irrespective of treatment actually received. Demographics and other relevant variables (e.g., number of acupuncture sessions received in the ACU arm) will be summarized by treatment arm using standard descriptive statistics. All data at all assessment time points will be summarized by treatment arm using standard descriptive statistics and plotted to visually assess trajectories over time. In the following subsections, we present specific analysis plans that are tailored to address our specific aim hypotheses, focus on single assessment time points, have relatively straightforward interpretations, and will be used to draw our primary conclusions regarding the Aims of this trial. However, our more general analysis approach will use more complex models to capitalize on the longitudinal nature of the study design and allow us to examine plots of the model-based trajectories of our outcome measures over time by study arm, giving us a visual overview of each outcome measure that incorporates all of the available data. For Aim 1, we will utilize generalized

linear mixed models (GLMM) to model the probability of opioid use across all time points (i.e. Day 7, 15, 30, and 90) as a function of study arm (ACU vs. OPI), time, the arm-by-time interaction, and randomization stratification variables.. For Aim 1 symptom burden, and for the continuous Aim 2 outcome measures, we will use linear mixed models (LMM) to similarly model those continuous endpoints over time. For both the GLMM and LMM analyses, we will use interaction terms between time and study arm to allow us to plot the arm-specific outcome trajectories over time. These statistical procedures (GLMM and LMM) account for within-subject correlations from repeated measurements in the same subjects and allow estimation of between-group differences without necessitating exclusion of participants with missing data.

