**14.2.2. Specific Aim 1 Analysis Methods.** To test Aim 1 hypotheses, we will test whether ACU has fewer opioid users compared to OPI at Day 7 (Hypothesis 1a) and at Day 90 (Hypothesis 1b) using separate but similar logistic regression models. Each model will predict opioid use at the given time point as a function of treatment arm (ACU vs. OPI), controlling for the randomization stratification variables (study site and cancer diagnosis). To test whether ACU reduces symptom burden at Day 7 compared to OPI (Hypothesis 1c), we will use a LMM to model the baseline and Day 7 MDASI-BMT Total Symptom Severity scores as a function of study arm (ACU vs. OPI), time (Day 0 and Day 7), and the arm-by-time interaction (coefficient of interest), controlling for the randomization stratification variables.

**14.2.3. Specific Aim 2 Analysis Methods.** For the Aim 2 hypotheses we will first test (Hypothesis 2a) whether mean pain scores among ACU patients were non-inferior to those among OPI patients (within a non-inferiority margin of 0.34 standard deviations) at Day 7 (key Aim 2 endpoint) using a LMM containing arm, time (Days 0 and 7), and the arm-by-time interaction as predictors, controlling for the randomization stratification factors. That is, if the mean Day 7 pain score in the ACU arm is not significantly ( $p < 0.025$ ) more than 0.34 standard deviations higher than the mean OPI pain score, then we will consider ACU to be non-inferior to OPI with respect to Day 7 pain control. A similar analysis will be performed for the Day 90 pain scores. For Hypothesis 2b, we will estimate mean differences (and 95% confidence intervals) between ACU vs. OPI side effect ratings, PROMIS-29 scores, and PROMS scores using separate linear mixed models for the Day 7 and Day 90 outcomes, controlling for the randomization stratification variables and baseline score (when relevant). We will have 80% power to detect unadjusted differences between study arms on these outcomes as small as 0.34 SD (i.e., Cohen's  $d = 0.34$ ) using two-sided tests and  $p < 0.05$ . By convention, this effect size is between a small (i.e.,  $d = 0.20$ ) and moderate ( $d = 0.50$ ) effect size. We will have power to detect smaller effect sizes in the covariate-adjusted regression analyses described above, but we have insufficient preliminary data on which to base estimates of these adjusted effect sizes.

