We will adjust all comparisons between the two treatment arms for the randomization stratification factors - study site and primary cancer diagnosis (MM versus HD versus NHL) - by including them as fixed effects in our statistical models.

**14.2.4. Exploratory Aim 1, Mediation.** We will explore potential causal mechanisms by testing mediation hypotheses (e.g. test whether the effect of treatment on Day 90 opioid use is mediated through the effect of treatment on Day 7 opioid use). We will use the approach to testing mediation hypotheses outlined in Imai, Keele, & Tingley (2010) in which a series of models are fit that allow estimation of the total, direct, and indirect (i.e., through the mediator) effects of treatment arm on Day 90 opioid use.

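### Transplantation setting is a stratification factor at randomisation but is missing from the covariate list of every planned comparison between arms

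*Combined protocol and SAP*

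**What the plan says.** Section 7.2 names three factors: "Randomization will be stratified by study site, primary cancer diagnosis (MM versus HD versus NHL) and transplantation setting (inpatient versus outpatient"). The method is permuted blocks within strata, 1:1.

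Section 14.2.2 defines the covariates of the two primary logistic models as "controlling for the randomization stratification variables (study site and cancer diagnosis"). The last paragraph of Section 14.2.3 extends that definition: "We will adjust all comparisons between the two treatment arms for the randomization stratification factors - study site and primary cancer diagnosis", entered as fixed effects.

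Elsewhere the plan refers to the stratification variables without listing them. The Analytic Methods row of Section 1.0 models outcomes "as a function of study arm (ACU vs. OPI), time, and randomization stratification variables", and Section 14.2.1 gives the longitudinal opioid model as including "time, the arm-by-time interaction, and randomization stratification variables".

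Transplantation setting is not named as a covariate anywhere in Section 14. It is also not among the effect-modification factors in Section 14.2.5.

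**The concern.** The plan's declared principle is to adjust for whatever was used to stratify. Two passages then list those factors and leave one out. An analyst working from Section 7.2 would include setting, and one working from Section 14.2.3 would not. Both could claim to be following the plan for two of the three primary tests.

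Stratifying on a prognostic factor balances it between arms. If the model then ignores that factor, its standard error does not credit the balance, so the test becomes conservative and some power is lost. The fitted odds ratio also changes meaning with the covariate list, because an odds ratio conditional on a prognostic covariate lies further from 1 than one that is not.

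The documents give reasons why setting could matter here. Under Section 13.1, opioid use comes from hospital drug records for inpatients and from pill counts for outpatients. Under Section 10.0, whether acupuncture is given on a day depends on the patient being in hospital or attending clinic.

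**Working it through.** **1. Factor lists side by side**

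| Place | Site | Diagnosis | Setting |
|---|---|---|---|
| 7.2, randomisation | yes | yes | yes |
| 14.2.2, primary logistic models | yes | yes | no |
| 14.2.3, all arm comparisons | yes | yes | no |
| 1.0 and 14.2.1 | not listed | not listed | not listed |

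There are 2 × 3 × 2 = 12 randomisation strata. The analysis model carries the site and diagnosis terms only.

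**2. The plan's own power figure**

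Inputs from Section 14.1: 25% vs 10% using opioids at Day 90, 135 evaluable per arm (150 × 0.90), two-sided alpha 0.02, so z = 2.326. The plan says "we will have 81% statistical power to detect this Day 90 difference between the two arms (i.e. 10% vs 25"%).

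- Pooled two-proportion formula: power = Φ{[d√n − z√(2p̄(1−p̄))] / √(p₁(1−p₁) + p₂(1−p₂))}.
- With d = 0.15 and p̄ = 0.175: [0.15 × 11.619 − 2.326 × 0.5374] / 0.5268 = 0.935, and Φ(0.935) = 82.5%.
- Wald test on the log odds ratio: ln 3 = 1.099, SE = √(1/(135 × 0.1875) + 1/(135 × 0.09)) = 0.349, and Φ(1.099/0.349 − 2.326) = 79.4%.

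The stated 81% lies between the two and is reproduced. It does not depend on the covariate list.

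**3. Size of the omission, by simulation**

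From the documents: 300 randomised, 10% attrition, 25% and 10% (25% in both arms under the null), alpha 0.02, stratified permuted blocks.

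Assumed, because the documents do not give them: site mix 60/40, diagnosis mix 60/10/30 (MM/HD/NHL), blocks of 4 or 6, no site or diagnosis effect on outcome, the inpatient share π, and the odds ratio of setting on opioid use (the same in both arms).

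For each arm the intercept a solves (1−π)·expit(a) + π·expit(a + ln OR) = overall rate p. Model: logit P(opioid use) = arm + site + diagnosis, with or without setting. Reject if |estimate/SE| for arm exceeds 2.326. There were 20,000 trials per cell.

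Results with half inpatient:

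| Setting OR | Power, omitted | Power, added | Gain (points) | Type I error, omitted |
|---|---|---|---|---|
| 1 | 83.0% | 83.1% | 0.1 | 0.019 |
| 2 | 83.3% | 83.9% | 0.6 | 0.020 |
| 3 | 83.0% | 84.4% | 1.4 | 0.016 |
| 6 | 83.5% | 86.5% | 3.0 | 0.014 |

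With setting added, type I error is 0.020 to 0.022. The Monte Carlo SE is √(0.02 × 0.98/20,000) = 0.001 for type I error and at most 0.14 points for the paired power difference.

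Trials significant only with setting added, against only with it omitted: 0.9% vs 0.3% (OR 2), 1.6% vs 0.2% (OR 3), 3.2% vs 0.2% (OR 6). The two readings of the plan therefore disagree in about 1.2%, 1.8% and 3.4% of trials.

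Power forgone at OR 2 / 3 / 6 under other assumptions:

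- 25% inpatient: 0.5 / 1.4 / 3.6 points.
- 75% inpatient: 0.4 / 0.8 / 1.3 points.
- Setting tied to diagnosis (30% of MM, 80% of HD/NHL inpatient): 0.3 / 1.1 / 2.2 points.
- Setting tied to site (80% inpatient at one, 10% at the other; 6,000 trials per cell): 0.4 / 0.6 / 1.4 points.
- Setting almost fixed by site (95% and 5%; 6,000 trials per cell): 0.0 / 0.3 points at OR 2 / 3.

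A separate simulation (4,000 trials per cell, 35% at the second site, half inpatient, blocks of 2, 4 or 6) agrees. Power goes from 82.1% to 82.1% at OR 1, 83.9% to 84.4% at OR 2, 83.7% to 85.6% at OR 4 and 84.3% to 88.1% at OR 8. At OR 4 the median treatment odds ratio is 0.32 without setting and 0.30 with it.

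**4. The linear mixed models**

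In the two-time-point models for symptom burden (H1c) and pain (H2a), the coefficient of interest is arm-by-time. A main effect of setting shifts both time points equally, so it should add little. In 2,000 simulated runs (300 patients, correlation 0.5, 10% missing at Day 7), the mean SE without / with setting was 0.123 / 0.123 when setting shifts Day 7 by 0.5 SD, and 0.134 / 0.134 at 1.0 SD.

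**The case against.** The best case against is that this is a wording mismatch of little consequence. At a setting odds ratio of 2 the loss is about half a point of power and no conservatism is visible (0.020 against 0.02). Losses near 3 points need an odds ratio around 6, which nothing in the documents supports. If setting largely follows site or diagnosis, those terms already absorb much of it. The mixed models gain nothing in precision. Adding setting moves type I error to between 0.020 and 0.022, so at the upper end a little of the recovered power reflects test size. Two passages also list two factors against one that lists three, so Section 7.2 could be the one that is out of date.

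Most of this stands as a limit on size. Conservatism is clear only when setting is strongly prognostic, and the low end of the range is close to zero. It does not remove the mismatch, because the text gives no reason for the omission and presents the shorter list as the stratification factors. Section 7.2 is the operative randomisation text, so it is the natural one to align to, subject to a check of what the randomisation system uses.

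**Conclusion.** The concern holds. Three factors are used at randomisation and two in the analysis, and the shorter list governs all arm comparisons, including the primary Day 7 and Day 90 opioid tests.

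The cost is modest and conditional: from nothing, if setting is not prognostic or nearly duplicates site, to about 3.6 points of power at an assumed odds ratio of 6 with 25% inpatient. The primary opioid tests fall below their nominal 0.02 when setting is strongly prognostic. Type I error is not inflated by the omission, neither arm is favoured, and the stated power and sample size are unaffected.

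The sizes rest on assumed values for the setting effect, the inpatient share, and the site and diagnosis mix. They are computed for Day 90 only; the plan itself expects similar power at Day 7. The case for change is that the remedy is close to free and makes the analysis match the randomisation. It does not rest on a showing of large harm.

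**What to change.** Reconcile Sections 7.2, 14.2.2 and 14.2.3 before analysis:

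- Confirm the factors in the randomisation system. If setting is one of them, add transplantation setting, as recorded at randomisation, as a fixed effect in Section 14.2.2 and in the Section 14.2.3 paragraph covering all comparisons. The generic references in Sections 1.0 and 14.2.1 then follow.
- If setting is left out on purpose, state the reason.
- If setting was not in fact used to stratify, correct Section 7.2.

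The gain is in the Day 7 and Day 90 logistic models and the longitudinal opioid model. In the two-time-point mixed models the addition serves consistency only.

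The cost is SAP wording and one binary covariate already held in the randomisation database, with no change to sample size, alpha allocation or data collection.

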For our sample size/power considerations for comparing symptom burden between ACU vs. OPI at Day 7, we calculated the smallest standardized effect size (aka, Cohen's d) we will be able to detect with 80% power, given our sample sizes of 150 in each of the two arms. To estimate this smallest detectable effect size, we used the methods of Lu, Luo, & Chen (2008), which describes sample size calculations for a class of analyses called the “mixed model for repeated measures” (MMRM) in randomized clinical trials with participant attrition. Our LMM analyses fall under this MMRM class of analyses. Using the “power.mmmr”

function from the R package “longpower”, we applied the formulas in Lu et al. (2008) to our study design and assumptions to derive the smallest detectable effect size for the coefficient of the time-by-arm interaction term in our LMM (with time including only the Day 0 and Day 7 assessments, see Section 14.2), which we transformed to represent the standardized mean difference (aka, Cohen’s  $d$ ) of the changes in symptom burden from baseline between the two arms at Day 7 post-HSCT. With 150 participants in each of the two arms, we will have power of 0.80 to detect an effect size for symptom burden as small as 0.41 (standardized difference, Cohen’s  $d$ ) at Day 7 between acupuncture vs. usual care, assuming 10% attrition, correlation between baseline and Day 7 symptom burden scores of 0.50, and two-sided alpha of 0.01. The MDASI-BMT Total Symptom Severity score does not have an empirically-established minimum clinically important difference (MCID). A research-based rule-of-thumb for PRO instruments lacking empirical MCIDs is to adopt a standardized difference of 0.50 as the MCID. Given our detectable effect size of 0.41, we will be able to detect a MCID in symptom burden between the two arms.

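### Hypothesis 1c is validly tested as a difference in change; adjusting for the baseline score already collected would cost almost nothing and could sharpen the test, by an amount the documents do not fix

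*Combined protocol and SAP*

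**What the plan says.** - **Section 14.2.2 (Hypothesis 1c).** A linear mixed model (LMM) of the baseline and Day 7 MDASI-BMT Total Symptom Severity scores contains arm, "time (Day 0 and Day 7), and the arm-by-time interaction (coefficient of interest), controlling for the randomization stratification variables". No baseline covariate and no common baseline mean is stated.
- **Section 14.1.** The powered effect is the standardized difference "of the changes in symptom burden from baseline between the two arms at Day 7". With 150 per arm and 80% power, the plan can detect an "effect size for symptom burden as small as 0.41", "assuming 10% attrition, correlation between baseline and Day 7 symptom burden scores of 0.50, and two-sided alpha of 0.01". For want of an empirical threshold, it chooses to "adopt a standardized difference of 0.50 as the MCID".
- **Section 14.1, on sample size.** "We based our sample size exclusively on having adequate power for the Day 90 comparison of opioid use".
- **Section 14.2.3 (Hypothesis 2b).** These secondary models are specified as "controlling for the randomization stratification variables and baseline score (when relevant"). The section adds: "We will have power to detect smaller effect sizes in the covariate-adjusted regression analyses described above".
- **Section 14.4.** The symptom burden analysis set is every randomized patient with a valid baseline score.
- **Sections 4.1, 7.2, 9.0 and 11.0.** The control is usual care without sham. Randomization follows registration, and baseline forms are completed within four weeks before chemotherapy. No rule places the baseline MDASI-BMT before disclosure of allocation, and the data collection table lists the baseline acupuncture expectancy form for the ACU arm only.

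**The concern.** Because arm enters as a free main effect, the model estimates a separate baseline mean in each arm, and the interaction subtracts the whole of any chance baseline difference from the Day 7 difference. Under randomization the true baseline means are equal. Subtracting the full difference is the most precise choice only when the regression slope of Day 7 on baseline is 1; otherwise it adds noise that an adjusted analysis avoids.

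Hypothesis 1c is a primary endpoint with the smallest share of alpha (0.01), and the sample size was not set for it. Its precision therefore depends on the choice of model. At stake is some power for moderate effects, not the validity of the test.

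**Working it through.** **Inputs from the plan (section 14.1):** 150 per arm at baseline; 10% attrition, so 135 per arm at Day 7; correlation r = 0.50; two-sided alpha 0.01; power 0.80. z-values: 2.576 + 0.842, or 3.4175 before rounding.

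**Assumed, because the documents give no SDs:** k = baseline SD / Day 7 SD. The Day 7 SD is set to 1.

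**Large-sample variance per arm, unstructured covariance**
- Planned interaction: (1 − r²)/135 + (r − k)²/150
- Adjusted (ANCOVA or constrained LMM): (1 − r²)/135 = 0.75/135 = 0.005556

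The difference between arms has twice this variance. Planned minus adjusted is 2(r − k)²/150, which cannot be negative and is zero when k = r.

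**Reproducing the plan's figure (k = 1).** The planned variance is 0.005556 + 0.25/150 = 0.007222. The SD of change is √(1 + 1 − 2 × 0.5) = 1, so the units agree. The detectable effect is 3.4175 × √(2 × 0.007222) = 0.411, against the stated 0.41.

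**After adjustment (k = 1).** 3.4175 × √(2 × 0.005556) = 0.360. Power at 0.41 is Φ(0.41/0.1202 − 2.576) = 80% planned and Φ(0.41/0.1054 − 2.576) = 91% adjusted.

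**Over assumed SD ratios.** Information given up is 1 − adjusted/planned variance. Detectable effects and power are in SD-of-change units, as in section 14.1; the SD of change is √(1 + k² − 2rk).

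| k | Planned variance per arm | Information given up | Detectable effect, planned / adjusted | Power at 0.41, planned / adjusted |
|---|---|---|---|---|
| 0.5 | 0.005556 | 0% | 0.416 / 0.416 | 79% / 79% |
| 0.7 | 0.005822 | 5% | 0.415 / 0.405 | 79% / 81% |
| 0.8 | 0.006156 | 10% | 0.414 / 0.393 | 79% / 84% |
| 1.0 | 0.007222 | 23% | 0.411 / 0.360 | 80% / 91% |
| 1.2 | 0.008822 | 37% | 0.408 / 0.323 | 80% / 96% |

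The loss keeps rising with k: 55% at 1.5 and 73% at 2.0. The stated 0.41 does not identify k, since every ratio from 0.7 to 1.2 rounds to it. In Day 7 SD units the adjusted figure is 0.360 throughout, and the planned one runs from 0.360 (k = 0.5) to 0.454 (k = 1.2).

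**At the plan's 0.50 benchmark.** Planned power is 93.7% to 94.7% over k = 0.5 to 1.2 in SD-of-change units. In Day 7 SD units it is 98.5% at k = 0.5 and 88% at k = 1.2.

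**Covariance structure.** A random-intercept model imposes equal variances, so its slope is b = rk/[(1 + k²)/2]. At k = 0.5, b = 0.25/0.625 = 0.4.
- Constrained: (1 + b²k² − 2brk)/135 = 0.84/135 = 0.006222
- Planned contrast, same structure: 0.006222 + [(1 − b)²k² − 2(1 − b)(rk − bk²)]/150 = 0.006222 + (0.09 − 0.18)/150 = 0.005622

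Here the constrained model's variance is about 11% larger. Break-even is near k = 0.7.

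**If allocation is known at baseline.** Assume a 0.2 SD reporting shift in one arm, equal SDs and no true effect.
- Shift persisting to Day 7: planned bias 0, type I error 0.010. Adjusted bias 0.10, type I error Φ(0.10/0.1054 − 2.576) ≈ 0.05.
- Shift at baseline only: planned bias −0.20, type I error Φ(0.20/0.1202 − 2.576) ≈ 0.18. Adjusted bias −0.10, type I error about 0.05.

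**The case against.** The strongest reply is that nothing is broken. The model and its power calculation agree, 0.41 lies below the adopted 0.50, and power there is already high. That stands: a reader might infer that 1c is invalid or underpowered, and the documents support neither.

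Other objections limit the point without removing it:

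- **The size is unknown.** A reader might take 37% as a ceiling, or 0.36 as established. Each holds only at one assumed ratio. Section 3.0 has mucositis pain peaking around Day 7, which may suggest a larger SD then than at baseline. That is an inference; if it is right, k is below 1 and the loss is at most 23%.
- **Precision depends on covariance.** Sections 14.2.1 and 14.2.2 name no structure, and a constrained random-intercept model can do worse than the planned contrast. The recommendation must therefore name ANCOVA or unstructured covariance.
- **Hypothesis 2b is a weak precedent.** A reader might see an inconsistency with 1c. But the remark in section 14.2.3 about smaller detectable effects compares adjusted with unadjusted differences, whereas 1c already uses baseline as a repeated response. Hypothesis 2a uses the same LMM form as 1c, so changing 1c alone would make those two Day 7 tests differ.
- **Baseline timing cuts both ways.** If allocation influences baseline answers, a persisting shift biases only the adjusted model, and a baseline-only shift biases the planned model more. The 0.2 SD shift is hypothetical, and the documents do not show that any such shift occurs.

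**Conclusion.** The point stands as an optional improvement, not an error. Adjusting for baseline is never less precise in large samples if done by ANCOVA or by a constrained LMM with unstructured covariance. The plan's correlation of 0.50 and 10% attrition fix everything except the SD ratio, and on that ratio the gain runs from nil to material. The case for acting is that the baseline score is already collected and the change is nearly free. The benefit lies mainly in effects smaller than 0.50 SD. The equal-baseline assumption also requires that baseline answers be given without knowledge of allocation.

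**What to change.** Before outcomes by arm are seen:

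1. Make the primary model for 1c one of these:
   - a constrained LMM with unstructured covariance: time and arm-by-Day 7 terms, no arm effect at baseline, and the stratification factors. This keeps the section 14.4 analysis set.
   - an ANCOVA of Day 7 score on arm, baseline score and the stratification factors. This uses only patients with a Day 7 score, so section 14.4 needs a matching edit.
2. Keep the planned LMM as a sensitivity analysis.
3. Update the model description in section 14.1. If the detectable effect is restated, give 0.36 as conditional on correlation 0.50 and equal SDs, with the range over SD ratios.
4. State that the baseline MDASI-BMT is completed before allocation is disclosed, and record both dates. If this cannot be assured, report both models.
5. Say whether Hypothesis 2a keeps its present form.

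Cost: a changed model statement, matching text in section 14.1 (and 14.4 for ANCOVA), a rule on baseline timing and two recorded dates. No extra patients or instruments are needed.
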